This will be a prospective randomized study comparing outcomes of pediatric patients who are treated with NAVA versus BiPAP respiratory support following cardiac surgery. Subjects will include pediatric CVCC patients who undergo cardiac surgery from October 2016 through October 2017 and who are up to 12 months of age. As patients recover from cardiac surgery, they are extubated and may require further respiratory support. If so, they receive CPAP support and then are transitioned to one of two modalities: either NAVA or BiPAP support. Both modalities are routinely used in the Children's CVCC, and the investigators will compare if one modality produces more favorable outcomes than the other. Following CPAP, enrolled subjects will be randomized to receive either NAVA or BiPAP, and their remaining clinical course will follow standard care. Specific measures following initiation of respiratory support will be collected, in addition to characteristics of the operative procedure and patient diagnoses. The study aims to compare duration of respiratory support, sedation requirements, and hospital length of stay between the two modalities.

Time Frame/Duration

This study will be conducted over an 18-month period to allow for subject enrollment, data collection, analysis, and manuscript preparation.

Activity		Month																
	1	2	3	4	5	6	7	8	9	10	11	12	13	14	15	16	17	18
IRB approval																		
Recruitment/enrollment																		
Data collection/ chart abstraction																		
Analysis																		

Manuscript preparation									

Analysis

Sample Size

We will enroll all consecutive patients who are eligible for inclusion in the 12-month enrollment period and consent to participation, up to 40 patients. An interim analysis will be performed after 20 patients are enrolled to assess means and variance of the primary outcomes, and reassess sample size.

Analytic Approach

Exploratory analysis methods will be used to describe the enrolled patient population, including mean and standard deviation for continuous variables such as length of hospital stay, sedation needs, and intubation as well as frequency and percentage for categorical variables such as STAT score and type of non-invasive PPV.

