For the continuous outcomes of interest (duration of non-invasive respiratory support, length of hospital stay and sedation needs), either a two-sample t-test or non-parametric Mann-Whitney U test will be used to compare those patients who received NAVA or BiPAP. For categorical variables, either a chi-square test or Fischer's exact test will be used to compare the two groups. Additional regression analysis will adjust for procedure severity.

Statistical significance will be defined as p < 0.05.

5. Subjects

Subjects

We plan to enroll 40 subjects 0 to 12 months of age at time of cardiac surgery over a 1 year period.

Identification of Subjects, Recruitment, and Enrollment

Potential subjects will be identified by monitoring the cardiovascular surgery schedule, and eligibility will be confirmed by the provider. Patients who meet all of the inclusion criteria and none of the exclusion criteria will be approached for consent by study staff. Not all cardiac patients receive NIV support postoperatively, and the decision to provide NIV support is not made by the provider until after the surgery. This will happen either while the patient is intubated, or immediately following extubation. Written informed consent will be sought from parents/guardians. Assent will not be sought in this young patient population. Patients who enroll will be assigned a unique study ID. A log of enrolled subjects will be maintained, and will only be accessible by approved study staff. The target enrollment is 40 patients.

Inclusion Criteria:

- Postoperative cardiac surgery patients admitted to the CVCC
- Recommended for NIV respiratory support following extubation, per provider discretion
- 0-12 months of age

Exclusion Criteria:

- Tracheostomy in place at time of cardiac surgery
- Chronic lung disease
- Pre-operative non-invasive respiratory support

6. Study Procedures

Data Requirements

The data elements will be collected by the research study staff from the subject's electronic medical record. These will include:

- Demographic Data (name, date of birth, age at admission, admission date/time, cardiac diagnosis, comorbidities)
- Operative Data (surgeon, date of procedure, intubation/extubation date/time, date/time returned to CVCC)
- Adverse Event Information (description of event and day post-cardiac surgery that the event(s) took place)

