- Medication Data (daily amounts of dexmedetomidine, fentanyl (total fentanyl and boluses of pca fentanyl), midazolam, morphine, lorazepam for up to 14 days postoperatively, date/time patient is on/off the above medications)
- Post-Operative Respiratory Support Data (type of non-invasive respiratory support used, date/time on off CPAP, date/time on/off biPAP/NAVA)
- Pain and Sedation Score Data (daily FLACC/SBS scores for up to 14 days postoperatively)
- Discharge Data (discharge date/time, length of hospital stay, survival at discharge, date/time of death [if applicable], cause of death [if applicable])

Visit Schedule

Eligible patients will be recruited during their admission to the CVCC. Upon enrollment, patients will be randomized to receive either NAVA or BiPAP. What respiratory modality the patient will receive will be determined by drawing a slip of paper from a sealed envelope. Following randomization and provision of respiratory support, patient care will be per standard care. Patient data will be only collected for the reference admission period. There will be no follow-up visits or activities required of the patient for this study following enrollment.

Drug/Device, Handling, Storage (If Applicable)

All devices in this study are currently used and stored in the CVCC. They will continue to be used as per CVCC SOPs.

7. Risks/Benefits

Potential Risks

Subjects will be randomized to respiratory support treatments that are already incorporated into standard care. The potential risks from these treatments are no more than those experienced as part of standard care. There is a risk associated with privacy of personal health information, and there is a risk of breach of confidentiality.

Methods to Minimize Risks

Both NAVA and BiPAP are non-invasive modalities that are safely used in standard care. Providers will follow SOPs for the use of NAVA and BiPAP support to minimize risks. If complications occur, standard care will be provided and patients will be treated accordingly. Electronic data will be stored on secure password-protected computers in limited access files, in a locked office suite. Any paper records will be stored in locked cabinets that only approved study staff have access to. This is a single-site study, and no identifiable patient data will be shared outside of the IRB-approved study staff. Any results from the study will be published in aggregate form, preventing any individual patient's data from being identified.

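### The outcome comparison is worded by device received, and nothing in the plan ties it to the randomised arms

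*Combined protocol and SAP*

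**What the plan says.** The test of the three continuous outcomes (duration of non-invasive support, length of stay, sedation) is set out in section 4, Analytic Approach: "either a two-sample t-test or non-parametric Mann-Whitney U test will be used to compare those patients who received NAVA or BiPAP". The next sentence compares categorical variables between two groups that it does not define. A further sentence plans a regression that adjusts for procedure severity.

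Other descriptions of the comparison also use exposure language. Study Design describes it by the device with which infants are treated, and the paragraph before the Research Question refers to outcomes after use of each device.

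Assignment is described separately. Study Design says "Following CPAP, enrolled subjects will be randomized to receive either NAVA or BiPAP". Section 6, Visit Schedule, says "Upon enrollment, patients will be randomized to receive either NAVA or BiPAP" and adds "What respiratory modality the patient will receive will be determined by drawing a slip of paper from a sealed envelope".

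On care after assignment, Study Design says of the unit "Both modalities are routinely used in the" CVCC. Visit Schedule says "Following randomization and provision of respiratory support, patient care will be per standard care". Section 7, Methods to Minimize Risks, says "If complications occur, standard care will be provided and patients will be treated accordingly".

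The supplied text does not mention intention-to-treat, an analysis population, or where to place an infant who uses both devices or neither. The Data Requirements list covers the type of support used and its on/off times, but not the assigned arm. Appendix 4, the data collection forms, is not shown.

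**The concern.** Randomisation protects the comparison only if infants are compared in the arms to which they were randomised. A rule based on the device received lets events after randomisation decide group membership. If sicker infants leave one arm more often than the other, that arm keeps the healthier infants and looks better on duration, sedation and stay. The direction depends on which arm loses them, so it cannot be known in advance.

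The literal rule is also incomplete. An infant who used both devices could be moved to the second, left out, counted in both groups, or kept with the device first started. These choices give different results, and with about 20 infants per arm a few placements can matter. If the choice is made after the data are seen, it becomes data-dependent.

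**Working it through.** **What can be checked.** No figure in the plan tests this point. The target of 40 comes without an effect size, standard deviation, power or allocation ratio, so it cannot be reproduced. The check asks how often a trial with no true effect gives p < 0.05 under each way of forming the groups.

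**Inputs from the plan.** Total enrolment 40; significance at p < 0.05; Mann-Whitney as one of the two named tests.

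**Inputs assumed.** 20 per arm; two-sided test; all switching patterns; correlation rho between severity and log duration of 0.3, 0.5 or 0.7.

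**Model.** log(duration) = log(48) + 0.8 × [rho × severity + √(1 − rho²) × noise], with 20,000 null trials per scenario and the Mann-Whitney normal approximation with continuity correction. That test uses ranks, so the 48 h and the 0.8 do not affect the null results. Simulation error near 5% is √(0.05 × 0.95 / 20,000) = 0.15 percentage points.

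**False-positive rate (%)**

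| Grouping and switching pattern | rho 0.3 | rho 0.5 | rho 0.7 |
|---|---|---|---|
| By assigned arm | 4.9 | 4.9 | 5.0 |
| As received, sickest 2 of 20 moved one way | 5.8 | 7.1 | 10.0 |
| As received, sickest 4 of 20 moved one way | 7.5 | 12.5 | 20.3 |
| Same 4 infants left out | 5.5 | 7.3 | 10.5 |
| Same 4 infants counted in both groups | 3.4 | 4.3 | 5.8 |
| Sickest 4 in one arm against 2 in the other | 5.0 | 5.0 | 5.8 |
| Sickest 4 each way | 4.4 | 3.9 | 2.8 |
| Chance switching, odds ratio 4 per SD of severity: 20% one way | 5.8 | 7.6 | 10.8 |
| Same odds ratio: 10% one way | 5.1 | 5.5 | 6.9 |
| Same odds ratio: 20% against 10% | 4.8 | 4.9 | 5.2 |

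When switching is unrelated to severity, the rate is 4.5 to 5.1%. If *received* means the device first started, a later switch does not change the group, and for that infant the result equals analysis by assigned arm.

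**Check with the other named test.** A separate t-test simulation at correlation 0.5 gives 8% with 2 of 20 moved and 13% with 4 of 20. The spurious differences are 0.16 and 0.28 SD in favour of the arm that the sick infants left.

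**Planned adjustment.** With the sickest 4 of 20 moved, a linear model adjusted for the same severity variable that drives switching gives 5.0 / 4.6 / 4.9%. Adjusting for a proxy that correlates 0.5 with it (assumed) leaves 6.5 / 9.7 / 15.6%.

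**Cost of analysing by assigned arm.** Assume a true NAVA/BiPAP duration ratio of 0.60, a log SD of 0.8, and switchers who lose the NAVA effect. With 2 of 20 NAVA infants switching, the expected ratio is 0.60^(18/20) = 0.63. With 4 of 20 it is 0.60^(16/20) = 0.66. Simulated power is 48% with no switching, then 40% and 33%.

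**The case against.** The strongest reply is that *received* is simply this protocol's word for assignment. Both Study Design and Visit Schedule speak of infants being randomised to receive a device, and the envelope determines what the infant will receive. That is a fair reading, perhaps the likelier one. A reader might infer that an as-treated analysis is planned, but the documents do not support that. They are ambiguous. What stands is that no sentence resolves the ambiguity.

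Second, no departure is documented. The statement about treating complications is general risk language, and no passage describes switching or gives a rate. With no departures, the two analyses are identical. This also stands. The text shows only that departures are possible.

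Third, the large figures need several conditions together: switching in one direction, strong dependence on severity, and moving the whole infant to the second device. Most other patterns in the table stay much closer to 5%. This is correct, and the 20% figure should not be read as a forecast.

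Fourth, the plan already adjusts for procedure severity. This helps only in part. Procedure severity is fixed by the operation and is not the same as condition after extubation. The regression is additional, so the unadjusted test remains.

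**Conclusion.** The point holds as a wording defect of low to moderate severity. The stated rule, taken at its word, groups a randomised trial by device received, and nothing else in the supplied text corrects it.

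The possible harm runs from none (no switching, or switching that is balanced or unrelated to severity) to a false-positive rate of about 6 / 7 / 10% with the sickest 2 of 20 moved one way and about 7.5 / 12 / 20% with 4 of 20. By assigned arm it stays at about 5%. All of these rates rest on assumed switching, 20 per arm and correlations of 0.3 / 0.5 / 0.7.

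A reader might go further and conclude that the trial's error rate is inflated, or that the assigned arm is not being recorded. Neither follows: no switching rate is given, and the data forms are not shown.

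**What to change.** 1. In the Analytic Approach, where the text reads "will be used to compare those patients who received NAVA or BiPAP", define the comparison instead as: all randomised patients, analysed in the arm to which they were randomised, regardless of device received. Apply the same groups to the categorical tests and the regression.
2. Keep any as-received comparison as a labelled sensitivity analysis, state where an infant who used both devices is placed, and report switchers and non-starters by arm.
3. Confirm that the assigned arm is recorded on the data forms.
4. For the assigned-arm analysis, count duration of non-invasive support across both bi-level devices, so that a switch does not end the count.

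Two neighbouring matters need their own treatment. How re-intubation, death and never starting support enter the duration outcome is an endpoint question that arises under any grouping. Study Design and Visit Schedule also differ on when randomisation takes place, and those passages must be reconciled.

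The cost is a few sentences and a form check, with no extra patients or visits. The statistical price is the dilution shown above: under those assumptions, power falls from about 48% to 40% or 33% if 2 or 4 of 20 NAVA infants switch.

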NAVA has recently been adopted for non-invasive respiratory support in the Children's Hospitals and Clinics of Minnesota CVICU, the cardiovascular care center (CVCC). Close to 10% of CVCC post-operative patients receive a form of bi-level NIV support, either NAVA or BiPAP. The frequency of NIV use in neonates (0 to 28 days of age) can be 30% or higher. We propose a randomized study to compare clinical outcomes following use of NAVA versus BiPAP in CVCC patients following cardiac surgery. Specifically, we will compare duration of NIV, duration of sedation, and hospital length of stay.

Research Question

Is the use of synchronized biphasic support with NAVA associated with shorter duration of noninvasive respiratory support, less sedation requirements, and reduced hospital length of stay compared to conventional BiPAP?

4. Study Design and Methodology

Aim 1: To assess whether the use of neurally adjusted ventilator assist (NAVA) is associated with a shorter duration of non-invasive respiratory support compared to conventional BiPAP. **Aim 2:** To assess whether the use of neurally adjusted ventilator assist (NAVA) is associated with less sedation requirements compared to conventional BiPAP.

Aim 3: To assess whether the use of neurally adjusted ventilatory assist is associated with reduced hospital length of stay compared to conventional BiPAP.

Hypothesis: Synchronized biphasic support with NAVA will be associated with shorter duration of non-invasive respiratory support, less sedation requirements, and reduced hospital length of stay.

Overview/Scope

Study Design

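### The main comparison of the three continuous outcomes is unadjusted; making a small prespecified model with severity and age primary would probably gain precision at little cost

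*Combined protocol and SAP*

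**What the plan says.** Section 4, Analytic Approach, gives the main comparison of the three continuous outcomes: "either a two-sample t-test or non-parametric Mann-Whitney U test will be used to compare those patients who received NAVA or BiPAP". Neither test uses a covariate. The next step is "Additional regression analysis will adjust for procedure severity", with no model type, no coding of severity and no other covariate. The threshold is "Statistical significance will be defined as p < 0.05", without stating sidedness.

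The size is fixed in section 5: "We plan to enroll 40 subjects 0 to 12 months of age at time of cardiac surgery over a 1 year period". No effect size, SD or power supports it. Section 4, Sample Size, leaves these to a look at the data: "An interim analysis will be performed after 20 patients are enrolled to assess means and variance of the primary outcomes, and reassess sample size".

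Section 6, Visit Schedule, describes allocation: "What respiratory modality the patient will receive will be determined by drawing a slip of paper from a sealed envelope". No stratification by age or severity is mentioned, and no allocation ratio.

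Section 6, Data Requirements, lists date of birth and age at admission. Its operative item reads "Operative Data (surgeon, date of procedure, intubation/extubation date/time, date/time returned to CVCC", with no STAT category, although section 4 plans to summarise STAT score. The background says of the youngest patients: "The frequency of NIV use in neonates (0 to 28 days of age) can be 30% or higher". It puts bi-level support at close to 10% of post-operative patients in the unit overall.

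**The concern.** Eligible infants run from newborns to 12 months and undergo operations of differing severity. If severity or age predicts how long support, sedation or stay lasts, an unadjusted test leaves that variation in the error term. The same 40 infants then yield a wider confidence interval than they need to.

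Because the envelope draw is not described as stratified, the arms may also differ by chance on these factors. As an illustration, if half of the 40 were neonates, the arms would differ by 20 percentage points or more in about 34% of randomisations. The p-value of the unadjusted test already allows for such imbalance on average. Adjustment corrects for it in the trial actually run.

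What is at stake is power and precision, in a trial with little of either to spare.

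**Working it through.** **Inputs.** From the documents: N = 40 and a 0.05 threshold. Assumed, because the documents do not say: two-sided testing, 20 per arm, and a joint R² of severity and age with the outcome between 0 and 0.30.

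**The plan's own figure.** N = 40 cannot be reproduced, since no effect size, SD or power is given.

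**Step 1: what the unadjusted comparison can detect.** The standard error of a difference, in SD units, is √(2/20) = 0.316. By the normal approximation, the effect detectable with 80% power is (1.960 + 0.842) × 0.316 = 0.886 SD. With the t distribution on 38 degrees of freedom it is 0.909 SD. Power (t) is about 34% for 0.5 SD and 69% for 0.8 SD.

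**Step 2: what adjustment does to the variance.** With k covariate terms, the variance of the treatment estimate is multiplied by about (1 - R²) × [1 + k/(N - k - 3)]. The bracket is the average cost of fitting the covariates. For k = 2 it is 1 + 2/35 = 1.057. The power column uses a true effect of 0.909 SD, where the unadjusted t-test has 80%.

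| Joint R² | Variance factor | Equivalent unadjusted N (40 / factor) | Power |
|---|---|---|---|
| 0 | 1.057 | 37.8 | 77.7% |
| 0.05 | 1.004 | 39.8 | 79.7% |
| 0.10 | 0.951 | 42.0 | 81.8% |
| 0.20 | 0.846 | 47.3 | 86.0% |
| 0.30 | 0.740 | 54.1 | 90.2% |

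The variance breaks even at R² = 1 - 1/1.057 = 0.054. With k = 5 (for example, several STAT indicators plus age) the bracket is 1 + 5/32 = 1.156 and the variance breaks even at 1 - 1/1.156 = 0.135, or about 0.15 once the lost degrees of freedom are counted. The model must therefore stay small.

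**Step 3: simulation on a rank scale.** Setting: 20 per arm, log-SD 0.8, duration halved (ln 2 / 0.8 = 0.866 SD), two binary covariates, rank-based ANCOVA against the unadjusted rank test. Unadjusted power is about 73-74%. Adjusted power is about 72% at joint R² 0, 76-77% at 0.10, 80-81% at 0.20 and 84-85% at 0.30. Type I error stays near 5% for both analyses.

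**Step 4: which covariate brings the gain.** Same setting, 8,000 runs per row, simulation error about 0.5 points.

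| R² severity | Further R² age | Unadjusted | Severity only | Severity + age |
|---|---|---|---|---|
| 0.10 | 0 | 74.0% | 77.6% | 76.4% |
| 0.10 | 0.05 | 73.5% | 77.1% | 78.3% |
| 0.10 | 0.10 | 73.3% | 77.3% | 80.8% |
| 0.20 | 0 | 73.4% | 81.7% | 80.8% |
| 0.20 | 0.05 | 73.2% | 80.7% | 81.9% |

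At severity R² 0.20, severity alone adds about 8 points. Age then changes power by about -1 point if it explains nothing more, +1 if it explains a further 5%, and +3 to +4 if it explains a further 10%.

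**The case against.** The strongest reply is that nothing here is wrong. Under randomisation the unadjusted test holds its type I error, an unadjusted main test with adjusted support is common and legitimate, and the severity regression that would bring most of the gain is already planned. The benefit rests on an R² that the documents do not give, and it becomes a small loss if the covariates are not prognostic. All of this stands, and it limits the point to efficiency.

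Three stronger readings are tempting and should be resisted.

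- *That the plan ignores strong predictors.* The background's 30% and 10% are frequencies of needing support. Every enrolled infant has already been recommended for it, and the 10% refers to all post-operative patients in the unit, not to infants up to 12 months. The figures do not show that age predicts duration, sedation or stay among infants who receive support.
- *That two analyses compete with neither in charge.* The regression is called additional, which already puts the unadjusted test first.
- *That STAT category will not be collected.* The printed list does not itemise it. However, Study Design promises characteristics of the operative procedure, the list is introduced as what the data will include, and the forms in Appendix 4 are not shown. This is something to confirm, not a gap.

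The familiar 40/(1 - R²), which gives 50 to 57 patients at R² 0.20 to 0.30, also flatters the case slightly. After the fitting cost the equivalents are about 47 and 54.

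**Conclusion.** The point holds as a cheap improvement, with moderate confidence. The plan's unadjusted test is valid but may forgo precision in a trial that can detect only large effects.

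The trade is lopsided in favour of adjusting: up to about 2 points of power lost if severity and age explain nothing, against roughly 7 points gained at a joint R² of 0.20 and 11 at 0.30. Below about 0.05 there is no gain. These sizes assume 20 per arm, two-sided 0.05, a log-SD of 0.8 and a halved duration; none of these comes from the documents except the threshold and the total of 40. The larger part of the gain comes from giving the severity adjustment first place. The case for age is weaker and rests on clinical plausibility and on its being collected already.

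**What to change.** Before outcome data are seen, amend the Analytic Approach as follows.

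- Make a regression the primary analysis of each continuous outcome, with terms for assigned arm, severity and age.
- Code severity from STAT category in one or two terms, and state the coding. Enter age in one term, for example continuous or log age, or neonate versus older.
- Use a log or rank scale, because durations are likely to be skewed. A log scale gives the effect as a ratio of durations. A rank scale is more robust but gives no effect in hours or days.
- Report the unadjusted test as supportive.
- Confirm that STAT category is on the data collection form, and add it if it is not.

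The cost is a few lines of plan wording, possibly one more field to abstract, about two degrees of freedom, and up to about 2 points of power if the covariates prove not to be prognostic.

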Over the years, an increased understanding of how a child's physiology interacts with a ventilation system has led to improved technologies. Whereas traditional ventilation modalities such as endotracheal intubation is invasive and can lead to tracheal damage with prolonged use (3), non-invasive ventilation (NIV) modalities avoid the risks associated with tracheal intubation. In addition, NIV can be used at an earlier stage compared to tracheal intubation, and facilitates gradual weaning when used intermittently (4). Two modalities that are widely used in intensive care units are continuous positive air pressure (CPAP) and bilevel positive air pressure (BiPAP). Both of these modalities operate using positive airway pressure to keep the trachea open. CPAP machines are set to deliver a continuous stream of air, while BiPAP machines offer a different level of pressure for inhalation versus exhalation. Collectively, use of these modalities and their benefits are well-documented, including improved gas exchange, decreased respiratory and heart rate, and decreased inspiratory work of breathing (5-8). Building on these strengths, neurally adjusted ventilator assist (NAVA) is emerging as an alternative form of the bi-level NIV with application in multiple settings.

With NAVA support, delivery of positive pressure is based on the electrical activity of the diaphragm (Edi) via a nasogastric (NG) catheter that is placed on the phrenic nerve, which runs along the esophagus. This concordance between the Edi and NAVA lends itself to synchrony between the patient and ventilator, as well as respiratory support that is proportional to the neural effort of the patient (9). Synchronous ventilation support results in decreased neural drive and

improved comfort in intubated patients (10, 11). Prior research has examined the use of NAVA in different patient settings, most notably the PICU and NICU as summarized in **Table 1**. These studies suggest NAVA may contribute to decreased sedation needs (12), improved synchrony (10, 13, 14), improved breath-to-breath mechanical variability (10), increased patient comfort (10), and reduction of wasted breathing efforts (13). In these populations, evidence supports the safety and feasibility of NAVA (12, 15).

Reference	Setting	Design	Intervention	Results
Kallio et	PICU	Randomized	Conventional ventilation (CV)	Ventilation duration: 3.3hrs NAVA and 6.6hrs
al 2014		controlled trial	or NAVA	CV (P=0.17); Sedation amount: 0.80units/hr

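### Any infant in whom NAVA cannot be used would surface only in the NAVA arm, and the planned comparison by device received would count that infant under BiPAP or lose it

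*Combined protocol and SAP*

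**What the plan says.** Section 5 (Subjects) lists three inclusion and three exclusion criteria. The one that concerns respiratory support is "Recommended for NIV respiratory support following extubation, per provider discretion". The exclusions are "Tracheostomy in place at time of cardiac surgery", chronic lung disease, and non-invasive support before surgery. None concerns the catheter, the diaphragm signal or suitability for either device. The same section states: "Patients who meet all of the inclusion criteria and none of the exclusion criteria will be approached for consent by study staff". It also says that "eligibility will be confirmed by the provider".

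The background describes what NAVA needs: "delivery of positive pressure is based on the electrical activity of the diaphragm (Edi) via a nasogastric (NG) catheter". It describes no such requirement for BiPAP.

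Section 6, Visit Schedule, states: "Upon enrollment, patients will be randomized to receive either NAVA or BiPAP". The modality is "determined by drawing a slip of paper from a sealed envelope". No check of the catheter or signal precedes the draw. After it, care follows the unit's usual practice, and nothing is said about an assigned device that cannot be used.

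Section 4, Analytic Approach, compares the continuous outcomes between infants grouped by the device they received. There is no intention-to-treat statement. Section 6, Data Requirements, does collect the type of support used and the on and off times for CPAP and for BiPAP or NAVA.

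**The concern.** Provider discretion in the entry criterion applies to the need for NIV, not to suitability for both arms. An infant in whom the catheter cannot be placed, or whose diaphragm signal is unusable, meets the written criteria and can be randomised. If the draw gives NAVA, the problem shows at the bedside. If it gives BiPAP, the same problem is never seen.

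The analysis wording decides what follows. Grouped by device received, an infant who fails NAVA and is switched leaves the NAVA group and joins the BiPAP group. If such infants tend to do worse, NAVA gains twice: it sheds a poor outcome and BiPAP takes one on. If the infant is dropped instead, NAVA gains once. Grouped by assignment, neither happens, and the cost is a diluted effect. With about 20 infants per arm, a few such cases could matter for all three outcomes: duration of support, sedation and length of stay.

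**Working it through.** **The plan's own figure.** The target of 40 cannot be reproduced, because no effect size, SD or power is given. It can only be inverted. Assume 1:1 allocation (20 per arm) and a two-sided 0.05 level; the plan states neither the ratio nor the sidedness. Then d = (1.960 + 0.842) × √(2/20) = 0.886, about 0.89, is detectable with 80% power (0.91 using the t distribution). This d is used below for illustration only.

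**Assumed inputs.** The documents give none of these:
- c, the share of infants who cannot be given NAVA: 5%, 10% or 20%.
- s, how much worse the outcomes of those infants are: 1 SD, varied from 0.5 to 1.5 SD.

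**Chance that it arises.** The probability of at least one such infant among 20 assigned to NAVA is 1 − (1 − c)^20.

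**Analysed as randomised.** Infants who switch are assumed to get no NAVA effect, so d becomes d(1 − c). Power = Φ(d(1 − c)√(20/2) − 1.960). For c = 10%: 0.797 × 3.162 − 1.960 = 0.561, and Φ(0.561) = 71%.

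**Analysed by device received.** The NAVA group keeps only suitable infants, 20(1 − c) on average. The BiPAP group has 20(1 + c), of whom 20c + 20c are unsuitable. With no true effect, the spurious NAVA benefit is s × 40c / [20(1 + c)] = s × 2c/(1 + c).

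**Dropped from the NAVA arm only.** The spurious benefit is s × c.

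Type I error comes from simulating t-tests with no true effect (40,000 runs per setting). The table takes s = 1 SD.

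| | c = 5% | c = 10% | c = 20% |
|---|---|---|---|
| At least one in the NAVA arm | 64% | 88% | 99% |
| Expected number of 20 | 1 | 2 | 4 |
| As randomised: type I error | 5% | 5% | 5% |
| As randomised: power (80% at c = 0) | 76% | 71% | 61% |
| As randomised: total N to restore 80% | 46 | 50 | 64 |
| By device received: group sizes, NAVA v BiPAP | 19 v 21 | 18 v 22 | 16 v 24 |
| By device received: spurious benefit (SD), formula | 0.095 | 0.182 | 0.333 |
| By device received: type I error | 5.9% | 7.8% | 14.4% |
| Dropped: spurious benefit (SD) | 0.05 | 0.10 | 0.20 |
| Dropped: type I error | 5.3% | 5.9% | 8.3% |

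**Sensitivity to s, by device received.** At s = 0.5 SD the type I error is 5.1%, 5.7% and 7.6% across the three values of c. At s = 1.5 SD it is 6.8%, 10.8% and 23.7%. At s = 0 the formula gives no bias: without a link to prognosis, only dilution or lost numbers remain.

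**The case against.** A reader might infer that infants unfit for NAVA are in fact being randomised and that one-sided crossover is happening. The documents do not support that. They report no such infant, rate, contraindication or switch, and they say that both devices are in routine use in the unit. Four further points count against a strong reading.

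- **Prognosis.** Nothing in the documents says that an infant with a poor signal recovers more slowly, still less one in whom a catheter cannot be placed. A bias favouring NAVA needs that link.
- **One-sidedness.** It holds for catheter or signal failure. The documents do not rule out BiPAP failures, so a net imbalance is not established.
- **Unseen screening.** The provider confirms eligibility, and section 7 refers to unit procedures that were not supplied. Only the titles of the study schema and data collection forms are visible, so a suitability item may exist there.
- **Design choice.** Comparing strategies in all infants recommended for NIV, with device failure counted as part of the strategy, is legitimate. The word for treatment received may also have been meant loosely.

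The first two points stand, and they limit the claim to a conditional one. The third stands only in part. The written criteria give the provider no suitability item to confirm, and the unit procedures are cited for using the devices, not for trial entry or analysis. The fourth in fact supports the main remedy: a strategy comparison needs analysis by assignment, which the plan does not state.

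**Conclusion.** The point holds as a conditional risk. Three features of the text combine: no entry requirement that either device could be given, no rule for an assigned device that cannot be used, and a comparison by device received. The NAVA-specific requirement comes from the protocol's own description.

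The size is unknown. Under the stated assumptions it is small at 5% unsuitable and material at 10% to 20%. Every value of c, s and d, the 1:1 ratio and the two-sided test are assumptions.

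It might also be inferred that a tighter eligibility rule alone would cure the problem. It would not: a judgement made before the draw cannot catch a signal failure first seen at the bedside. The bias is removed mainly by analysing infants as assigned; the pre-draw confirmation limits the dilution that remains.

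**What to change.** 1. In section 4, Analytic Approach, replace the comparison by device received with a primary comparison by assigned group. State that infants whose assigned device could not be used, or was changed, stay in that group. Report device failures and switches by arm, using the type-of-support and on/off times already collected. This needs no new data.
2. In sections 5 and 6, have the provider record, before the envelope is opened, that in their judgement either arm could be given. Log infants who do not meet this as screen failures. The clinical content of that judgement is for the investigators.

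The cost is a short amendment and one item on the enrolment form. The downsides are dilution if failures prove frequent, a few infants lost from a pool of at most 40, and results that apply to infants judged suitable for both devices. The documents do not allow an estimate of how many infants the confirmation would exclude.
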